## 5.6 Data Analysis

**Sampling plan: Power analysis.** To ensure sufficient variability in our outcomes, and in turn increase the power to test study hypotheses, we focused our Specific Aims on overall risk for recidivism (i.e., PICTS GCT total scores) and functioning on health-related risk factors, rather than recidivism per se (e.g., rearrest), as the latter may have a low base rate within the 12-month study period. Based on meta-analyses and studies of MRT mechanisms, we expect a medium effect size (Cohen's  $f^2=.15$ ) in multiple regression models testing condition (UC vs. MRT) as a predictor of recidivism risk and the health-related outcomes. However, given the planned moderation analyses, we calculated the power to detect small effect sizes (i.e.,  $f^2=.02$ ). To account for having patients at three sites, power analyses using G\*Power were based on having six cells (two conditions per site). A sample size of 292 (146 in each condition) will provide 80% power to detect a small effect size at an alpha of .05 (two-tailed test). To account for the moderators, we calculated the available power and effect size that could be detected in a regression model, given (a) our projected sample size, and (b) the addition of six more predictors in the model (i.e., the three moderator variables listed above and three interaction terms between these moderators and the variable of condition). Based on an N of 292 and alpha of .05, we would have 80% power to detect an  $f^2$  of .07, a small-to-

medium size effect. We are predicting 20% attrition at the follow-ups. This was the rate of attrition in prior longitudinal studies of project team members of Veteran treatment samples with high rates of criminal histories. Thus, we will recruit a total of 365 patients (183 in each condition, with rounding). If attrition reaches 30%, we will still have 80% power to detect an  $f^2$  of .08.

**Procedures to locate and follow patients.** To ensure high follow-up rates (>80%), we will adhere to well established procedures used by members of the project team for locating and following mental health patients in longitudinal studies who are homeless and have extensive criminal histories. Specifically, a form will be included in the baseline assessment to obtain information on patients' mailing address, home/work/cell phone numbers, and employment information; contact information from a parole/probation officer, or case manager; and up to three additional individuals to be used in the event that contact with the participant is lost. This information will be collected and updated at all assessments. To complete follow-ups, project staff will persist in their efforts (for a minimum of three documented attempts) to locate a participant for the duration of the data collection period. These efforts will include mailing reminder cards to participants two weeks in advance of their scheduled follow-up interview. The card will include an 800 telephone number for participants to call. Although some participants will be homeless, in our past studies, homeless participants often contacted us for follow-ups or were successfully contacted by project staff when returning for VA appointments. We also have connections with local homeless shelters and providers from VJP and VA supportive housing programs, which will greatly aid our ability to track participants. A participant will be considered "not located" only if s/he is not contacted at the time of the data lock. Once located, repeated attempts (a minimum of three) will be made to contact participants by phone and/or mail.

We are confident we will be able to achieve an 80% response rate, given that we have achieved follow-up rates above 80% in prior longitudinal studies (e.g., 92% at a 1-year follow-up; 84% at a 2-year follow-up) using the same rigorous tracking procedures as proposed here with populations that had high rates of justice involvement and homelessness at intake. Further, in our current HSR&D study of Telephone Monitoring with dually-diagnosed psychiatric inpatients, 98% of participants have access to a phone for research assessments. To maximize retention, we will collect follow-up data via either telephone or in-person interviews, which will include visits to jails or prisons to interview participants who are incarcerated. We will use "peer trackers" to assist with locating clients, as they have social networks to track down participants and have been highly effective in our past studies. "Peer trackers" will also utilize the program, VistAWeb, on a national level to locate difficult to reach participants for the follow-up assessments.

**Aim 1: Analytic plan.** The project data will be analyzed at the Palo Alto VA by Drs. [name] and [name]. We hypothesize that those in the MRT (vs. the UC) condition will (1) have lower overall risk for criminal recidivism, and (2) better health-related outcomes (i.e., substance use, mental health, housing, and employment); and (3) the effects of MRT on reduced risk for recidivism and better health-related outcomes will be mediated in part by greater likelihood of completing the MH RRTP and utilizing SUD/mental health continuing care services. To test these hypotheses, we will do the following:

Examine distributions. Generalized mixed-effects regression models (GLMM) will be conducted. However, prior to conducting these models, we will examine the distribution of the outcome and

predictor variables. If non-normality in variable distributions is observed for the baseline comparisons between the UC and MRT conditions, we will use data transformation or nonparametric tests of equality between groups. One of the benefits of GLMM is its capacity to accommodate different conditional distributions for each outcome variable by choosing appropriate link and variance functions within GLMM.

Examine baseline equivalence. We will use independent group t-tests and chi-square tests for continuous and categorical variables, respectively, to determine whether patients assigned to the UC and MRT conditions are comparable at baseline on (a) age, race/ethnicity, marital status, education, and income; (b) PICTS GCT scores; (b) substance use, mental health, housing, and employment status; (c) SUD/mental health treatment utilization and mutual-help group participation; and (d) percent incarcerated in the past 5 years, number of months since the most recent criminal justice event (i.e., charged or released from incarceration), and extent of criminal history (i.e., scores on a composite of number of charges, number of times incarcerated, and total number of months incarcerated). We do not anticipate baseline differences; however, if they are detected, the variables on which groups differ will be controlled in the regression analyses.

Compare the UC and MRT conditions on study outcomes. We will use GLMM regressions to compare the UC and MRT conditions on overall risk for recidivism (PICTS GCT scores); and substance use (ASI alcohol and drug composites; TLFB scores), mental health (ASI psychiatric composite; PHQ-9 and PCL-5 scores), housing (ASI–number of months in a stable residence), and employment status (ASI employment composite) over the study period. GLMM models permit modeling of repeated-measures data; do not require that all participants be measured at all time points to be included in analyses; and apply to continuous, dichotomous (e.g., MH RRTP completion), and Poisson-distributed outcomes (e.g., number of SUD/mental health outpatient visits).

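### The detectable effects quoted for the moderator model (f² = .07, or .08 at 30% attrition) are not those of the single interaction terms the plan will test, and the power paragraph does not say which test they describe

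*Combined protocol and SAP*

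**What the plan says.** All the figures are in section 5.6, under the power analysis. The plan expects f² = .15 for condition but, because moderators will be examined, computes power for f² = .02 on a six-cell layout (two conditions at three sites), two-sided at the 5% level: "A sample size of 292 (146 in each condition) will provide 80% power to detect a small effect size".

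It then allows for moderation by "the addition of six more predictors in the model", namely three moderators and their three interactions with condition. It continues: "Based on an N of 292 and alpha of .05, we would have 80% power to detect an" f² of .07. Recruitment of 365 allows for 20% attrition, and the paragraph closes with a reassurance: "If attrition reaches 30%, we will still have 80% power to detect an" f² of .08.

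The moderator analysis, later in section 5.6, uses one binary moderator (incarcerated or not in the past 12 months) and two continuous ones (months since the last justice event, and a criminal-history index). Each is crossed with condition, and subgroup effects are probed if any interaction term is significant. The paragraph names G*Power, but not the procedure, the tested degrees of freedom or the total number of predictors.

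**The concern.** Two things do not fit.

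- Each planned moderator test concerns one coefficient. Six extra predictors cost such a test only six denominator degrees of freedom out of nearly 290, so they cannot move its detectable effect from .02 to .07 at the same N. The two statements must describe different tests, and neither test is named.
- The .07 and .08 are offered as the sensitivity of the moderator model, so a reader will apply them to the interactions.

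At stake is how the moderator results, and the stated tolerance to 30% attrition, are interpreted. A reader would conclude that only small-to-medium moderation is detectable and that f² = .02 is covered at 80%. For a single-outcome 1-df test, the first is too pessimistic and the second too optimistic.

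**Working it through.** **Inputs** (section 5.6): N = 292; alpha .05, two-tailed; 80% power; f² = .02, .07 and .08; six cells; six added predictors, of which three are 1-df interactions; 365 recruited. Check: 292/0.8 = 365. At 30% attrition, 365 × 0.7 = 255.5, so N is 255 or 256.

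**Formula** (fixed-model regression): noncentrality λ = f²·N; numerator df u = terms tested; denominator df = N − k − 1, with k the total predictors. Power is the probability that a noncentral F(u, N − k − 1, λ) exceeds the central 95% point. Solve for f² at 80%.

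**Step 1: try to recover the plan's figures with a whole-model test (u = k).**

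| Predictors | f² at N = 292 | f² at N = 255 / 256 |
|---|---|---|
| 11 (six cells as 5 df, plus 6) | .0596 | .0686 / .0683 |
| 12 (six cells counted as 6, plus 6) | .0616 | .0710 / .0707 |
| 14 | .0655 | .0755 / .0752 |
| 16 | .069 | .080 / .079 |

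Ordinary rounding gives .06 and .07 for 11 or 12 predictors; .07 and .08 need 14 to 18. With 12 predictors and rounding up, both stated values appear: f² = .06 has 78.7% power at N = 292, and f² = .07 has 79.3% at N = 255, so the next two-decimal values are .07 and .08. Power at those values is then about 86%.

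**Step 2: the moderator tests (k = 11, alpha .05, 80% power).**

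| Test | u | f² at N = 292 | f² at N = 255–256 |
|---|---|---|---|
| One interaction | 1 | .027 | .031 |
| Three interactions jointly | 3 | .038 | .043 |
| All six added terms | 6 | .048 | .055 |

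For one interaction at N = 292, λ = .0271 × 292 = 7.91 on (1, 280) df. At the stated effects, power for one interaction is not 80%: λ = .07 × 292 = 20.44 gives 99.5%, and λ = .08 × 255 = 20.40 gives 99.4%. The stated .07 is .07/.027 ≈ 2.6 times the single-interaction value.

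**Step 3: the f² = .02 statement as a 1-df test.** λ = .02 × 292 = 5.84. Power is 67.3% with 5 predictors and 67.3% with 11, so the six added terms make no visible difference. At N = 256, λ = 5.12 and power is 61.6%; at N = 255, λ = 5.10 and power is 61.4%. Testing all six cells together (5 df) at f² = .02 gives 41%.

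**Step 4: how far repeated measures could change Step 3.** The documents give no within-person correlation ρ, so it is assumed here. For a between-group comparison of the average of m = 3 measurements, λ = f²·N·m/(1 + (m − 1)ρ), on (1, 290) df. With f² = .02 and N = 292 the numerator is 17.52.

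| Assumed ρ | λ | Power |
|---|---|---|
| .3 | 17.52/1.6 = 10.95 | 91% |
| .5 | 17.52/2.0 = 8.76 | 84% |
| .8 | 17.52/2.6 = 6.74 | 73% |

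This is illustrative only: one of the three measurements precedes randomisation, and the plan's model compares slopes.

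**The case against.** The other side has four good arguments.

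- **A reader might infer that .07 and .08 are arithmetic errors.** The documents do not support that. The total predictor count is not given, and a 12-predictor whole-model test rounded up returns both values. A larger count is also conceivable, since the moderators enter outcome models that carry time terms: condition 1, site 2, condition by site 2, time as a three-level factor 2, condition by time 2 and the six added terms make 15, which gives .067 and .078. The power paragraph mentions no time terms, so this is only a possibility.
- **A reader might state as fact that the figures come from a whole-model test.** That is the closest match at alpha .05 and 80% power, but other settings come near too, for example 90% power with 9 predictors (.070 and .081).
- **A reader might infer that the trial is too small, or that 395 analysed patients are needed.** For a single-outcome 1-df test at f² = .02, 395 is indeed the N for 80% power. But the planned analysis is a mixed model over three time points using all available data, and its power depends on a correlation that the documents do not give.
- **The discrepancy is conservative for moderation.** Recruitment of 365 comes from 292/0.8, not from .07 or .08, and the moderators are not among hypotheses 1a–1c.

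All four stand as limits on the point. None makes .07 and .08 the detectable effects of a single interaction, and none reconciles them with the f² = .02 statement as the same kind of test.

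**Conclusion.** The point holds in a limited form. No 1-, 3- or 6-df test at alpha .05 and 80% power has detectable effects of .07 and .08. For the single interactions the plan will act on, the values are about .027 and .031, so the paragraph understates sensitivity to moderation by a factor of about 2.6 on the partial f² scale. The f² = .02 claim errs the other way if read as a 1-df regression test: about 67% rather than 80%, falling to about 62% at 30% attrition. Whether it also fails for the planned repeated-measures model cannot be settled from the documents; the illustration runs from 73% to 91%.

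These results assume a single-outcome regression with fixed predictors and unadjusted alpha. This is a reporting correction worth making. It does not show that the sample size is wrong, and f² = .027 is far below the .15 the plan expects for condition.

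**What to change.** Revise the power paragraph in section 5.6, leaving N unchanged:

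1. Replace .07 and .08 with the detectable partial f² at 80% power: .027 (.031 at 30% attrition) for one interaction, and .038 (.043) for the three jointly.
2. For every figure, state the G*Power procedure, the tested degrees of freedom and the total number of predictors.
3. Restate power at f² = .02 as about 67% (about 62% at 30% attrition) for a single-outcome 1-df test, labelled as an approximation. Alternatively, give the repeated-measures power with the effect tested and the within-person correlation assumed, over a range such as .3 to .8.

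The cost is a few sentences and a short recalculation, with no change to design, recruitment or analysis. The downside is that the stated power at f² = .02 may become less favourable.

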Health-related functioning. We will use the ASI to assess substance use, and mental health, housing, and employment status at baseline. In addition to items on housing, the ASI assesses functioning in several problems areas, e.g., alcohol use, drug use, psychiatric, and employment. In each domain, items measure the number, extent, and duration of problems (lifetime and past 30 days). Composite scores are produced from sets of items that are standardized and summed (range from 0 to 1; higher scores indicate poorer outcomes), which provide internally-consistent indices of patient status in the relevant domains in the past 30 days. Prior work supports the validity of self-reports on these areas. To further assess substance use, the Time-Line Follow Back (TLFB) will be administered. The TLFB is a retrospective, calendar-based measure of substance use, which has been validated for administration in-person or via phone and will provide information on quantity and frequency of substance use in the 6 months prior to the baseline assessment (i.e., percent days of use; percent days abstinent; most consecutive days using; most consecutive days abstinent). To further assess psychiatric status, the PHQ-9 will be administered to assess symptoms of major depression, and the PTSD Checklist (DSM-V version) will be used to assess symptoms of PTSD. VA records will be used to gather SUD and mental health diagnoses on patients at the time of admission to the MH RRTP, per ICD-9 codes linked to the appropriate bedsection code in the inpatient files.

SUD/mental health treatment and mutual-help history. We will use the ASI to assess participants' treatment history (i.e., any care [yes/no]; number of visits over the lifetime and past 12 months) for SUD (outpatient, residential, pharmacotherapy) and mental health (outpatient, inpatient, residential). Information on VA health services utilization in the past 12 months will be collected via patient records for these domains of care. Data on non-VA health care utilization will be collected to help determine whether the two condition arms are balanced and ensure that any changes in utilization of VA services are not due to changes in non-VA care. To measure attendance (yes/no; number of meetings) and involvement in mutual-help groups (lifetime, past 12 months) we will use items from the Alcoholics Anonymous Inventory.

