Examine moderators. For the direct effects of condition (UC, MRT) on study outcomes (overall risk for recidivism; and substance use, mental health, housing, and employment status), we will test three moderators of these effects: (a) incarcerated or not in the past 12 months; (b) number of months since the most recent criminal justice event (i.e., charged or released from incarceration); (c) an index of extent of criminal history (i.e., a z-scored composite of number of charges, number of times incarcerated, and total number of months incarcerated in lifetime). The continuous moderators (number of months since the most recent criminal justice event, and index of criminal history) will be zero-centered. The main effects of these moderator variables and the interaction terms between condition (UC, MRT) and each moderator will be entered into the same regression models described above. If any interaction terms are significant, conditional moderators will be evaluated to assess the direction and magnitude of effects within subgroups (e.g., re-entry subgroup).

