**Aim 2: Analytic plan.** De-identified audio-files of the staff and patient interviews will be transcribed. The transcription will be performed by a professional medical transcription agency specifically chosen for this study. Drs. [name] and [name] will review the transcripts of these interviews, and take detailed notes using the structure of the RE-AIM Planning Tool. With feedback from project team members, we will create tables to summarize and categorize the barriers/facilitators of MRT implementation at the system, provider, and patient levels, and include potential solutions and potential-to-leverage columns that contain evidence-based implementation tools to be considered for more widespread usage of MRT. These analyses will reduce and display the data. In conjunction with the tables, we will identify a small set of themes within each domain of the RE-AIM framework that signify triangulated findings (e.g., factors that would facilitate and maintain a program's use of MRT in a way that fits within the clinical and administrative infrastructure of the facility). The purpose will be to capture in-depth information on patient, provider, and contextual factors that will facilitate or hinder the successful implementation of MRT. Such factors will be used to inform post-hoc interpretation of project findings and guide development of action plans to be tested in subsequent implementation projects. If Aim 1 hypotheses are not supported, we will use this analytic approach to identify barriers associated with delivery of MRT during the RCT, and what modifications to MRT could

be made to maximize effectiveness. Such information will be shared with our operational partners to guide their future efforts to reduce recidivism risk among JIVs.

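### Hypothesis 1b is tested on 8 to 11 measures, and three moderators on every outcome, with no multiplicity control and no rule for when 1b counts as supported

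*Combined protocol and SAP*

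**What the plan says.** Section 3.0 lists 1a and 1b as parallel hypotheses. 1a is tied to a single score, PICTS GCT. 1b names four domains (substance use, mental health, housing, employment) and no lead measure in any of them.

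Section 5.6, in the paragraph comparing the conditions, gives the 1b measures as "substance use (ASI alcohol and drug composites; TLFB scores), mental health (ASI psychiatric composite; PHQ-9 and PCL-5 scores", followed by months in a stable residence and the ASI employment composite. It does not say which TLFB scores are meant. Section 5.5 lists four in its baseline description: "percent days of use; percent days abstinent; most consecutive days using; most consecutive days abstinent".

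On moderators, Section 5.6 says "we will test three moderators of these effects", where the effects are those on recidivism risk and on all the health outcomes. Any significant interaction is then followed by subgroup probing. The mechanisms paragraph likewise carries any significant direct effect of MRT forward to a mediation analysis.

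Alpha appears once, in the power paragraph: the planned sample "will provide 80% power to detect a small effect size at an alpha of .05 (two-tailed test". The supplied text contains no multiplicity adjustment, no testing order and no statement of how many measures or domains must be significant for 1b to be supported.

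**The concern.** 1b is a formal, directional hypothesis with several measures in two of its four domains. Without a lead measure or a rule for support, an analyst who follows the plan can report 1b as supported on whichever measure reaches significance. The same section acts on single significant results: one significant direct effect is enough to start a mediation analysis, and one significant interaction is enough to start subgroup probing. A chance finding could therefore acquire both a proposed mechanism and a subgroup story.

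The moderator tests are not labelled exploratory. The power paragraph gives them as a reason for the sizing: "given the planned moderation analyses, we calculated the power to detect small effect sizes". Elsewhere Section 5.6 does use exploratory language, for the comparison of 12 with 24 sessions, so its absence here is noticeable.

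**Working it through.** **The plan's own figure.** The plan states: "A sample size of 292 (146 in each condition) will provide 80% power", for f² = .02. It adds: "We are predicting 20% attrition at the follow-ups". The inflation reproduces: 292 / (1 − 0.20) = 365. The power does not follow from the stated regression inputs. A 1-df F test with noncentrality f² × N gives 67% power at N = 292 and needs N = 395 for 80%. A repeated-measures between-groups test does match, but only with unstated settings (for example, three measures correlated .6 give N = 290, and 80.3% power at 292). This is a separate matter. It does not affect the error rates below, which depend only on the number of tests, the alpha and the correlation.

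**Counts**, taking one treatment test per measure, since baseline, 6 and 12 months enter one model:
- 1b with TLFB as one score: ASI alcohol, ASI drug, TLFB, ASI psychiatric, PHQ-9, PCL-5, housing, employment = 8.
- 1b with four TLFB scores: 8 + 3 = 11.
- Interactions, adding PICTS GCT: 9 × 3 = 27, or 12 × 3 = 36.

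**Error rates if no effect exists.** A two-sided .05 test favours MRT by chance with probability .025. For k independent tests, the chance of at least one result favouring MRT is 1 − .975^k, and of at least one in either direction 1 − .95^k.
- 1b favouring MRT: 1 − .975^8 = 18.3%; 1 − .975^11 = 24.3%.
- Interactions, either direction: 1 − .95^27 = 75.0%; 1 − .95^36 = 84.2%.

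The documents give no correlations between outcomes. The dependent cases below assume one common correlation between all test statistics and were simulated with 400,000 draws.

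| Family | Independent | .3 | .5 | .7 |
|---|---|---|---|---|
| 1b favouring MRT, 8 tests | 18.3% | 15.3% | 12.5% | 9.7% |
| 1b favouring MRT, 11 tests | 24.3% | 19.0% | 15.2% | 11.1% |
| Any interaction, 27 tests | 75.0% | 63.1% | 48.4% | 32.7% |
| Any interaction, 36 tests | 84.2% | 71.7% | 54.8% | 36.3% |

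Percent days of use and percent days abstinent are near-complements. Dropping one leaves 10 tests: 1 − .975^10 = 22.4%.

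**Power after adjustment**, for a simple two-arm comparison with 146 per arm and d = 2√f². This is not the planned mixed model, and its 68% at alpha .05 is below the plan's stated 80%.
- f² = .02, d = 0.283: d / √(2/146) = 2.417. Power is Φ(2.417 − 1.960) = 68% at alpha .05, and Φ(2.417 − 2.498) = 47% at .05/4 = .0125, the strictest Holm step.
- f² = .15, d = 0.775: above 99.9% at either alpha.
- Smallest d with 80% power: (1.960 + 0.842) × √(2/146) = 0.33 at alpha .05; (2.498 + 0.842) × √(2/146) = 0.39 at .0125.

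**The case against.** Several points against a stronger reading are sound.

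- A reader might infer that a false claim of health benefit is likely. It is not. The chance of any significant result over 11 tests is 1 − .95^11 = 43%, but this counts results favouring usual care, which cannot support a directional hypothesis. The relevant figure is at most 24%.
- A reader might carry the high moderator figures over to 1b. An interaction is a subgroup signal, not a claim that 1b holds, and 3 of the 36 concern PICTS GCT, which is not a health outcome.
- Eleven is an upper count. Section 5.6 says only TLFB scores, and the list of four stands in the baseline description. Hence the range of 8 to 11.
- Testing each measure at .05 is an inference from the power paragraph. So is the idea that any one measure would do: the four domains are joined by a conjunction, and requiring all four would not inflate error. The plan does not choose between these readings.
- A reader might take the Aim 2 plan to say that support for 1b steers the advice given to partners. Its text covers only the opposite case: "If Aim 1 hypotheses are not supported, we will use this analytic approach to identify barriers". It sets out no action after a positive result.

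These points limit the size of the problem but do not remove it. No passage supplies a rule for support, and single significant results do trigger further analyses.

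**Conclusion.** The concern holds in limited form. With no lead measure, rule for support or adjustment, reading any one significant measure as support gives 1b a false-positive rate in MRT's favour of 18% to 24% under independence. At assumed correlations of .3 to .7 it is about 11% to 19% for 11 tests. That is roughly four to ten times the nominal 2.5% (11.1/2.5 = 4.4; 24.3/2.5 = 9.7). A spurious moderator finding is more likely than not over 36 tests unless the tests are strongly correlated: 84% if independent, about 55% at .5 and 36% at .7.

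These figures assume no true effect, .05 two-sided for every test, one test per measure and an equal correlation that the documents do not supply. They omit the further analyses in Section 5.6, such as the one restricted to patients who attended at least the first MRT session. The change is worth making because it is cheap; the flaw does not undermine 1a.

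**What to change.** Amend Section 5.6, before outcome data are examined by arm, to say:
- PICTS GCT is the single primary outcome, tested at .05 two-sided.
- For 1b, one measure is named in each of the four domains. Housing and employment already have one each, so a choice is needed only for substance use and mental health. The four are tested with Holm at .05, and benefit is claimed only for domains that pass. This controls error within 1b, not jointly across 1a and 1b.
- The remaining scores are supportive and are reported with confidence intervals. Only one of percent days of use and percent days abstinent is used.
- Moderator analyses are exploratory, with false-discovery-rate control applied before any subgroup is probed.

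The cost is analysis-plan wording: no added patients, visits or data. The downside is lower power for small effects on single 1b measures, about 68% falling to 47% at f² = .02 at the strictest Holm step in the two-arm approximation. At the plan's expected f² = .15 the loss is negligible. Holm with one measure per domain is one valid choice among several; the essential step is to fix a procedure and a rule for support in advance.
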